8.2 Assessment of an Adverse Event

8.2.1 Relationship (Causality/Relatedness)

The causality assessment is the determination, according to the investigator's clinical judgment, of the existence of a reasonable possibility that the investigational product (IP) caused or contributed to an adverse event.

If the investigator or delegated sub-investigator is unsure about whether or not the study product caused or is related to the event, then the event will be handled as "related" to the study product for reporting purposes of the trial. If the causality assessment is "unknown but not related" to the study product, this should be clearly documented in the source documents.

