8.0 ASSESSMENT OF SAFETY

8.1 Definitions

8.1.1 Adverse Event

An **Adverse Event (AE)** is defined as any new event that may jeopardize the patient which the study investigator physician perceives may be directly related to the enrolment in the pilot study or to the assigned arm. Adverse events are not study related if they are related primarily to the underlying disease. All AEs are to be documented and assessed for relatedness. If related to the study intervention and occurring from baseline up to 24 hours (by the final visit), the AE will be recorded on the eCRF and coded as per the most recent edition of the Common Terminology Criteria for Adverse Events (CTCAE).

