8.1.5 Serious Adverse Event (SAE)

A serious adverse event (SAE) in the study is defined as:

- a) any event that is fatal or immediately life threatening, permanently disabling, severely incapacitating, or requires prolonged inpatient hospitalization, or
- b) any event that may jeopardize the patient and requires medical or surgical intervention to prevent one of the outcomes listed above, AND
- c) which the attending physician perceives may be directly related to enrolment in the study, or to the assigned arm.

SAEs will be considered to be study-related if the event follows a reasonable temporal sequence from the study intervention and could readily have been produced by the intervention. Adverse events are not study related if they are related primarily to the underlying disease.

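### Sections 8.1.1/8.1.5 and 8.2.1 classify an injury-driven event with a possible blanket contribution in opposite ways, which mainly affects whether a non-serious, non-skin AE reaches the eCRF

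*Combined protocol and SAP*

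**What the plan says.** **Inclusive rule (8.2.1).** The investigator judges the "existence of a reasonable possibility that the investigational product (IP) caused or contributed to an adverse event". Doubt is resolved towards the product: an assessor who cannot decide whether it played a part must class the event as related when reporting. The section also allows an event to be documented as *unknown but not related*.

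**Main-cause exclusion (8.1.1 and 8.1.5).** Both sections carry the same sentence: "Adverse events are not study related if they are related primarily to the underlying disease".

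**Positive SAE rule (8.1.5).** An SAE counts as related if its timing fits and it "could readily have been produced by the intervention". This stands directly before the exclusion, with no order of precedence.

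**SAE definition (8.1.5(c)).** It includes the condition "which the attending physician perceives may be directly related to enrolment in the study"; relation to the allocated treatment is given as an alternative. In 8.1.1 the corresponding view is that of the study investigator physician.

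**What relatedness decides.** Under 8.1.1, eCRF entry is conditional: "If related to the study intervention and occurring from baseline up to 24 hours (by the final visit), the AE will be recorded". Under 8.3.2, an event is a SUADR if it is serious, unexpected, and either related or not excludable as related.

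**A further exclusion (8.2.5).** At the investigator's discretion, events thought to be probable manifestations of the underlying condition do not count as AEs and need not be recorded.

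**The concern.** One rule asks for the main cause, the other for any plausible contribution. These are different thresholds, and an event can fail the first while passing the second.

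In this population that is foreseeable. Every participant has a massive hemorrhage protocol activated, so severe injury is a candidate main cause for many events. Section 8.1.2 also recognises that some participants may be sedated, and cites the manufacturer's caution about people who cannot feel or regulate heat. Events with a mixed cause are therefore the ones on which the causality rule needs to be clear.

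At stake is the consistency of the AE record. Two assessors who agree on the facts of a case could each follow the protocol and make different eCRF entries. The trial is meant to inform a larger one, so its device-related AE listing should rest on one definition.

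**Working it through.** There is no planned figure to reproduce, and the point depends on no numeric design input. The check applies each rule to the same set of cases and then follows the result to the decisions that use it.

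**Step 1: apply both rules.**

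| Case | 8.1.1 / 8.1.5 | 8.2.1 | Conflict? |
|---|---|---|---|
| A. Injury is the only cause; product ruled out | Not study related | Not related | No |
| B. Blanket is the main cause | Exclusion does not apply; related | Related | No |
| C. Main cause not settled; assessor unsure about the product | Exclusion not triggered; silent on doubt | Handled as related | No |
| D. Injury judged the main cause; blanket a reasonably possible contributor | Not study related | Related | **Yes** |
| E. As D, but assessor unsure whether the blanket contributed | Not study related | Handled as related | **Yes** |

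The rules part only once the injury has been judged the main cause and a contribution from the blanket has not been ruled out (D and E).

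**Step 2: look for text that reconciles them.** None was found. Section 8.2.1 does not carry over the main-cause exclusion, and 8.1.1 and 8.1.5 do not mention contribution. Section 8.2.1 does not spell out that a contributing product makes an event related, but under a heading on relationship and relatedness a positive finding can mean nothing else. Nor does the vocabulary separate the rules. Sections 8.1.1 and 8.1.5 speak of relation to the study and 8.2.1 of relation to the product, yet 8.1.1 itself uses relation to the intervention to decide eCRF entry. I take the underlying disease to mean the injury, which is the natural reading in a trauma trial.

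**Step 3: follow the consequence for cases D and E.**

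| Decision | Does it depend on the conflict? |
|---|---|
| eCRF entry of a non-serious, non-skin AE (8.1.1) | Yes. It is conditional on relatedness, and the 8.2.5 exclusion gives a second route to non-recording. |
| SAE status (8.1.5) | Partly. Item (c) makes perceived relatedness part of the definition and assigns it to a different assessor. |
| Reporting SAEs to the sponsor (8.3.5) | Largely not. Deaths and immediately life-threatening events go whether or not related, and other SAEs whatever the relationship. The second safeguard still needs the event to have met the SAE definition. |
| SUADR classification (8.3.2) | Little. Its own threshold agrees with 8.2.1; what remains is the uncertainty over seriousness through 8.1.5(c). |
| Skin redness and burns (3.6, 5.4.1, 7.2) | No. They are safety outcomes, collected at the study visits and summarised by arm without a relatedness filter. |

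**The case against.** The strongest reply is that this is a wording tension in a single-centre feasibility pilot with little riding on it. Much of that stands. The one device harm that the protocol expects, mild burns, is captured as an outcome. Section 8.1.1 asks for all AEs to be documented and assessed, 8.2.5 sends AE information to the source documents, and 8.3.5 covers SAEs. Sections 8.1.1 and 8.1.5(c) also use permissive language: it is enough that the physician perceives the event *may* be related. But that permissive test sits in the same sections as the main-cause exclusion, so it adds to the tension instead of removing it. Source documentation also does not settle what goes on the eCRF.

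Several stronger readings are tempting but unsupported:

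- **That 8.1.5 admits an SAE as related only if the intervention could readily have produced it.** The text says if, not only if. It is a sufficient condition, and the conflict does not rest on it.
- **That every doubtful event changes class.** Where the main cause is unsettled, the exclusion is not triggered and 8.2.1 decides (case C).
- **That the exclusion could empty the device safety record.** The skin outcomes and the SAE route in 8.3.5 argue against this.
- **That a difference in related-event percentages can be stated.** Section 7.2 plans no such rate, and the documents give no event count to compute one from.
- **That *unknown but not related* contradicts the unsure rule.** It can mean that the cause is unknown but the assessor is confident that it was not the product.

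Open-label assessment is a declared feature of the design and is not part of this point.

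**Conclusion.** The inconsistency is real and narrow. For an event judged mainly due to injury, with a blanket contribution reasonably possible or not ruled out, 8.1.1/8.1.5 and 8.2.1 give opposite answers and the protocol sets no precedence. The main consequence is inconsistent eCRF recording of non-serious, non-skin AEs. A lesser one is uncertainty over SAE status through 8.1.5(c). The number of events affected cannot be estimated from the documents. No feasibility outcome, listed safety outcome, planned analysis or sample-size input depends on it. It should be corrected because it is cheap to correct and because it governs what the AE listing means. The conclusion assumes that the underlying disease means the injury, and that a finding of contribution under 8.2.1 means related.

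**What to change.** Use one causality rule for AEs, SAEs and SUADRs. The 8.2.1 rule is the natural choice because 8.3.2 already agrees with it.

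1. In 8.1.1 and 8.1.5, delete the main-cause exclusion, or restrict it with wording such as: *an event due to the underlying injury is not study related where a contribution from the study product has been ruled out*.
2. In 8.2.5, put the discretionary exclusion for manifestations of the underlying condition under the same restriction. Otherwise the same events could still go unrecorded by that route.
3. Name the investigator or delegated sub-investigator as the assessor throughout, replacing the attending physician in 8.1.5(c).
4. Keep *unknown but not related* only if it is defined as: *cause unknown, product contribution ruled out*.

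The cost is an edit to Section 8, and a few more events classed as related and entered on the eCRF. No change to the design, sample size or analysis is needed.

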8.2.2 Expectedness

Events are classified as unforeseen or unexpected if the nature, severity, or frequency is not consistent with the risk information set out in Section 9.1.2 or the Product Monograph (PM) or label.

8.2.3 Seriousness

Events are classified as serious if associated with effects threatening the life or physiological functions of a participant. Refer to the definition for "Serious Adverse Events" in section 9.1.5.

8.2.4 Severity

The term "severe" is often used to describe the intensity (severity) of a specific event (e.g. mild, moderate, or severe myocardial infarction); the event itself, however, may be of relatively minor medical significance (such as severe headache). This is not the same as "serious," which is based on participant/event outcome or action criteria usually associated with events that pose a threat to a participant's life or functioning. The terms "serious" and "severe" are not synonymous. Seriousness (not severity) serves as a guide for defining regulatory reporting obligations.

To assess the severity of an adverse event the investigators will use the following:

- the National Cancer Institute (NCI) Common Terminology Criteria for Adverse Events (CTCAE)

8.2.5 Adverse Event Recording

Investigations into potential adverse events should be done during each contact with a participant.

Investigations may be done through specific questioning and, as appropriate, by examination.

Information on all adverse events should be recorded promptly in the source document, and assessed by an investigator in a timely manner allowing sufficient time to meet required reporting timelines for SAEs and serious unexpected adverse drug reactions (SUADRs) if needed. Adverse event CRFs should be completed using source documents by a delegated research team member in a timely manner/within 15 days of site awareness. All clearly related signs, symptoms, and abnormal diagnostic procedures should be recorded in the source document, though should be grouped under one diagnosis. Each diagnosed

adverse event should then be categorized in accordance with the revised NCI Common Terminology Criteria for Adverse Events (CTCAE).

The following are not considered AEs and therefore do not require recording:

- Pre-existing diseases or conditions identified and recorded at screening/baseline unless, at the discretion of the investigator, the disease or condition worsens in severity or frequency
- At the discretion of the investigator, events considered likely manifestations of the underlying disease or that commonly occur in the study population independent of study drug exposure
- Elective medical or surgical procedures.

8.3 Procedures for Reporting a Serious Adverse Event and Unanticipated Events

8.3.1 Investigator reporting: Notifying the REB

Serious adverse events and unanticipated events should be recorded and reported to the REB in accordance with local reporting requirements and timelines.

8.3.2 Investigator reporting: Notifying the Sponsor

The investigator is responsible for reporting SAEs and SUADRs to the sponsor (Sunnybrook Research Institute) in accordance with applicable regulations and reporting requirements and timelines.

Events that are assessed to be **serious and unexpected and related or cannot be ruled out as related** to the investigational product are considered SUADRs. Reporting for SUADRs should include a description of the event in sufficient detail to allow for a complete medical assessment of the case and independent determination of possible causality. The minimum information required includes at least one identifiable participant, one identifiable reporter, one serious reaction, and one suspect product.

Additionally, for SAEs and SUADRS, a Suspect Adverse Reaction Report – CIOMS I Form (Appendix B) must be completed by the investigator and forwarded to the Sponsor within 24 hours of site awareness. Information on other possible causes of the event, such as concomitant medications and illnesses should also be provided as soon as is made available.

8.3.3 Sponsor Reporting of SUADRs: Notifying Health Canada

The regulatory sponsor is responsible for reporting SUADRs to regulatory authorities in accordance with local expedited reporting requirements and timelines. In addition, the Sponsor will complete the ADR Expedited Reporting Summary Form and submit this form in conjunction with the completed CIOMS Form to the appropriate Health Canada directorate.

8.3.4 Sponsor Reporting of SUADRs: Notifying Sites

The regulatory sponsor is responsible for distributing expedited reports of SUADRs to each investigator for submission to local Ethics Committees within 15 days of sponsor awareness.

8.3.5 Reporting and Entry Timelines

Study investigators will report SAEs to the sponsor within the following timelines:

- All deaths and immediately life-threatening events, whether related or unrelated, will be recorded and reported to the sponsor within 24 hours of site awareness.
- Serious adverse events other than death and immediately life-threatening events, regardless of relationship, will be reported to the sponsor within 72 hours of site awareness.

Adverse event information will be entered into the CRF in a timely manner and **no later than 15 days** from the time the investigator becomes aware of the event.

Serious adverse event information will be entered into the CRF in a timely manner/**within 72 hours** from the time the investigator becomes aware of the event.

9.0 Early Termination and Reasons for Withdrawal

While it is not anticipated to cause discomfort, patients may find that they are not able to continue with the study product due to the ongoing heat. Patients are permitted to withdraw consent at any time if they desire and will not undergo further trial investigations if they do so. Participants withdrawing from the study should be contacted by the study research team requesting a final visit and to follow up with any unresolved adverse events. Once withdrawn from the study, no further study procedures or evaluations should be performed, or additional study data collected. However, every effort should be made to obtain permission to document the reason for withdrawal and to collect participant outcomes, such as survival data up to the protocol-described end of participant follow up period, where possible. Any data collected prior to the withdrawal of consent may be retained and used by the sponsor. If the patient withdraws from the study, the research team will notify the patient's most responsible physician.

9.1 Data Collection and Follow-up for Withdrawn Participants

Patients will be asked to continue with follow-up of body temperature and laboratory tests. It is important to continue to follow these patients and capture outcomes that occur once they have discontinued study intervention to determine feasibility. Through telephone calls and emails, every effort will be made to obtain permission to document the reason participants withdrew consent and to continue collecting the body temperature and laboratory values previously mentioned. Patients who have had at least one of the blankets applied will be included in the per-protocol analysis.

10.0 ETHICAL ISSUES

10.1 Ethical conduct and ethical issues

Approval for patient accrual must be obtained from research ethics board (REB) at SHSC before patient recruitment can begin. Any additional correspondence with REB must be maintained by the research coordinator/assistant.

10.2 Informed Consent

Due to the clinical condition of the patients during initial presentation, screening and enrollment will be at the discretion of the Trauma Team Leader on an urgent basis. When the patient is able to safely converse, study personnel will approach the Most Responsible Physician (MRP) for permission to approach the patient. With permission, the research coordinator will then approach enrolled patients, g to introduce the trial and conduct the informed consent discussion. By being invited into the patient's circle of care with the permission of the MRP, study personnel will Introduce the rationale for the study, the anticipated risks and benefits of participation, and their rights as a study participant (including withdrawal at any time). Capable participants will be offered an opportunity to ask questions and

consult with their family and/or their physician before final decision. If the patient is deemed medically incapable, consent will be obtained from the substitute decision maker (SDM) . One signed copy of the informed consent will be placed in the participant's medical record, another copy given to the participant and the original kept in the study file with the research coordinator. If the participant does not wish to continue to participate, the reason for declining will be documented and the patient will be considered a screening failure (failure to provide informed consent).

11.0 STUDY ADMINISTRATION

This will be a single-site study, conducted at Sunnybrook Health Sciences Centre. The Research Coordinators, supervised by the Principal Investigator, will be responsible for trial coordination, site training, site start-up/activation, document management, supply management, database development, data management and statistical analysis. Study data and patient surveys will be entered and maintained on a secure password protected database developed using REDCap (www.projectredcap.org) and will be accessible via the Internet for data entry purposes.

11.1 Arrangements for day-to-day management of the trial

The research coordinator will be responsible for this aspect of the study, including system checks, maintenance, and data back-up. Patient data will be collected as enrollment occurs and entered into the electronic case report forms. Data queries will be generated monthly. A bi-weekly status report will include an update on the recruitment and status of all randomized patients. Monthly to bi-monthly audit and feedback meetings will be held. Protocol violations will be audited and recorded on designated Protocol Violation Forms.

Clinical research coordinators will work with investigators on start-up activities (REB applications; study contract; organizing study materials; local in-services). Thereafter, research coordinators will screen, consent and enrol patients, complete case report forms, and respond to data queries.

11.2 Quality Assurance

Study data will be maintained on a secure password protected database accessible from the world-wide-web. Quality control will be ensured by oversight by the research coordinator at Sunnybrook Research Institute, who will review the electronic data for all participants on a regular basis for completeness and consistency.

Quality and completeness of data entry will be reviewed as soon as possible after data entry, within five business days of data entry for the first five participants randomized, and within 15 days of data entry thereafter. Data queries generated by identification of incomplete or inconsistent data will be raised and should be resolved by the study coordinator or PI in a timely manner. Corrections or changes in the data management system are tracked with the retention of the original data and the corrected data with the date of data entry and submitting personnel.

13.0 DATA HANDLING AND RECORD KEEPING

13.1 Confidentiality

Information about study participants will be kept confidential and managed according to the requirements of the Personal Health Information Protection Act of 2004 (PHIPA) and the Research Ethics Board. PHIPA outlines the rules for the collection, use and disclosure of personal health information. The Act requires each participant to consent to the collection, use and access of personal health information (PHI), unless consent is waived by the REB. As consent is required, each participant will be informed of the following:

- What PHI will be collected during this study
- Who will have access to that information and why
- Who will use or disclose that information
- The rights of a research participant to revoke their authorization for use of their PHI.

In the event that a participant revokes authorization to collect or use PHI, the investigator may use all information collected prior to the revocation of participant authorization. For participants that have revoked authorization to collect or use PHI, attempts should be made to obtain permission to collect at least vital status (i.e. that the participant is alive) at the end of their scheduled study period.

13.2 Source Documents

Source data/documents are original documents, data and records in a clinical study that are necessary for the reconstruction and evaluation of the study. Original documents and data records in this study include, but are not limited to:

- worksheets
- hospital records
- medical records
- memorandum
- participants' diaries or evaluation checklists
- pharmacy dispensing records
- copies or transcriptions certified after verification as being accurate and complete
- participant files and records kept at the pharmacy
- entries entered directly into the source documents

Research coordinators will maintain appropriate medical and research records for this study, in addition to regulatory and institutional requirements for the protection of confidentiality of participants. If electronic source data documents are printed it should be signed and dated by the investigator to confirm content and filed with other source documents.

The investigator(s) and research team members listed on the Task Delegation Log (TDL) will have access to participant medical records and will collect only the information needed for the study. Sponsor delegated monitors, representatives of institutional committees and regulatory authority representatives of the country in which the study is being conducted will also have access to examine records for the purposes of quality assurance reviews, audits and evaluation of study safety and progress.

